Protocol Title: A randomized, double-blind, dose-ranging trial of subcutaneous sodium deoxycholate injections with or without low dose triamcinolone and low dose lidocaine for reduction of submental fat with reduction of pain and swelling

# 1. Background and Rationale

Submental fat accumulation is a common concern amongst patients presenting for a cosmetic dermatologic consultation. Liposuction was employed previously for aesthetic improvement. However, alternative non-invasive techniques such as cryolipolysis, focused ultrasound, radiofrequency, and injectable sodium deoxycholate (SDOC) have been developed to meet the increasing demand for minimal downtime procedures. Patient experience with SDOC has been less than optimal, however, with approximately only 1 in 4 patients returning for more than one treatment.

Subcutaneous pure synthetic SDOC (KybellaTM, Allergan) gained FDA approval for reduction of submental fat in June 2015. When injected into submental fat, Kybella(TM) ultimately results in focal adipocytolysis and focal destruction of fat cells. An excellent pharmacokinetic safety profile has been demonstrated, with no measurable increases in serum cholesterol, triglycerides, or free fatty acids detected 24 hours following injection [1, 2]. Furthermore, four large phase III clinical trials to date have demonstrated the efficacy of Kybella(TM) in the reduction of submental fat [3].

Despite the documented safety and efficacy of Kybella(TM), many patients experience a variable degree of edema and pain following subcutaneous injection which can sometimes last for several days to weeks and can be a significant cause for concern. The mechanism of edema and pain secondary to Kybella(TM) injection is unknown but *thought to be an irritant response directly related to deoxycholate and not subsequent adipocyte lysis and death*. This edema and pain is thought to be a major factor contributing to the relatively small percentage of patients returning to complete the full treatment regimen. This study proposes to answer the question of whether immediate swelling and pain can be reduced to increase patient tolerance and improve patient experience without reducing the longer term low level inflammatory component which results in visible and measurable submental fat reduction.

A previous study was performed using high doses of a corticosteroid. This double-blind, randomized study utilized triamcinolone acetonide (TMC), a corticosteroid compound, in conjunction with Kybella(TM) showed that the addition of TMC reduced the incidence of early edema and tenderness, but negatively impacted long term efficacy and produced cutaneous changes of steroid atrophy in 7 (47%) of the 15 patients treated with TMC [4]. In the study, 2.0 mL of 2 mg/cm2 of Kybella(TM) was mixed with 0.05 mL of 40 mg/mL of TMC, and was delivered in up to 50 injections spaced 1.0 cm apart at 0.25 mL/injection for a total dose of up to 100 mg of Kybella(TM). As the tolerability of Kybella(TM) remains a significant issue in patient care, perhaps lower concentrations of TMC would be effective in reducing side effects without compromising treatment efficacy and causing steroid atrophy.

#### 2. Study Objective & Hypothesis

The primary objective of this study is to evaluate the efficacy, edema and pain associated with Kybella(TM) injections of the upper neck in the treatment of submental fat with low concentrations of triamcinolone acetonide plus low doses of lidocaine. An evaluator blinded to the study will grade the level of improvement of the submental fat. Safety will also be assessed.

The Working Hypothesis: The combination of Kybella(TM) and with very low dose triamcinolone acetonide is effective in the reduction of immediate edema associated with Kybella(TM) injections and does not adversely affect the previously demonstrated long term reduction of submental fat. Addition of 0.1% lidocaine will provide immediate pain relief for a better patient experience. As 1% lidocaine is already injected just prior to Kybella injection as per current treatment protocol, there is no anticipated effect from low dose 0.1% lidocaine other than anesthesia.

# 3. Study Design

This is a two-site randomized, double-blind comparison trial of Kybella(TM) injections with or without triamcinolone acetate for the reduction of submental fat. 30 subjects will be enrolled into the trial (15 subjects per site). At each site, 5 will be randomized to receive Kybella(TM) injections alone whereas 10 will receive Kybella(TM) plus differing doses of triamcinolone acetate in the following way:

- 1. Group 1 (5 patients per site): Kybella(TM) alone: 2 mg/cm^2 of Kybella(TM) with **0.2 mL** of 1% lidocaine with no epinephrine plus 0.2cc saline to the non-TMC group to maintain equal concentrations in each injection so that the final Kybella concentration per vial will be 10mg/1.2mls or 1.6mg per 0.2 cc injection point will be delivered in up to 50 injections spaced 1.0 cm apart at 0.2 mL/injection for a total maximal dose of up to 100 mg of SDOC.
- 2. Group 2 (10 patients per site): Kybella(TM)+TMC at **1.0 mg/mL**: 2.0 mL of 2 mg/cm^2 of Kybella(TM) will be mixed with **0.2 mL of 10 mg/mL** of triamcinolone acetate, **0.2 mL of 1% lidocaine with no epinephrine** and then delivered in up to 50 injections spaced 1.0 cm apart at 0.2 mL/injection for a total dose of up to 100 mg of SDOC using a 30 gauge (or smaller) 0.5-inch needle. The final Kybella concentration per vial will be 10mg/1.2mls or 1.6mg per 0.2 cc injection point

The treatment area will be bounded superiorly by a line 1 cm inferior to the mandibular margin, laterally by the sternocleidomastoid muscles, and inferiorly by the hyoid bone. The subjects and evaluating investigator will be blinded to the treatment, thus maintaining double-blind status. By nature of the varying volumes of injection, the treating investigator will be unblinded to the treatment. A series of 3 injection sessions will be performed spaced 4 weeks apart. No lidocaine will be injected prior to injections to prevent further dilution of injected KybellaTM as it will be

premixed with KybellaTM. Chilling with cold will be the method of pain reduction for needle insertion.

Canfield Vectra 3D imaging will be performed at baseline and final visit (Appendix C) with analysis and calculation of volumetric changes performed at baseline and final visit. Photos will also be taken with the Intellistudio at all other visits. Follow up visits will be performed 3 and 5 days after each injection session to assess for side effect and tolerability profile. After the final injection session, additional follow up visits will be performed at days 90 and 180 to assess for efficacy. Subject weight will be recorded at baseline and at end of study.

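### The SDOC dose figures in Section 3 do not agree with each other, and the Group 2 triamcinolone strength is given on a different volume basis from the SDOC strength beside it

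*Combined protocol and SAP*

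**What the plan says.** For both groups, Section 3 (Study Design) gives a nominal area dose of 2 mg/cm2, points 1.0 cm apart, 0.2 mL per point, at most 50 points and at most 100 mg. In Group 1 the wording is "in up to 50 injections spaced 1.0 cm apart at 0.2 mL/injection for a total maximal dose of up to 100 mg of SDOC". Both groups also carry a diluted strength; for Group 2, "the final Kybella concentration per vial will be 10mg/1.2mls or 1.6mg per 0.2 cc injection point".

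Group 2 is labelled "Kybella(TM)+TMC at 1.0 mg/mL". Its recipe is 2.0 mL Kybella, 0.2 mL of TMC at 10 mg/mL and 0.2 mL of 1% lidocaine. Group 1 receives the lidocaine "plus 0.2cc saline to the non-TMC group to maintain equal concentrations in each injection".

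Section 1 (Background and Rationale) describes an earlier study, which it calls high dose, in which 2.0 mL of Kybella "was mixed with 0.05 mL of 40 mg/mL of TMC" and was given in "up to 50 injections spaced 1.0 cm apart at 0.25 mL/injection", also up to 100 mg. It reports steroid atrophy in 7 of 15 TMC patients and a loss of long-term efficacy. It then reasons that "perhaps lower concentrations of TMC would be effective in reducing side effects without compromising treatment efficacy and causing steroid atrophy". Section 2 calls the present TMC dose very low.

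**The concern.** The concentration, volume per point, number of points and maximum dose are tied together by multiplication, so they can be checked against each other. As printed they do not agree: the maximum fits undiluted product, while the concentration and per-point dose fit the diluted mix. A reader cannot tell from Section 3 how much SDOC a fully treated subject receives.

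The TMC strength has a related problem. In one bullet, SDOC is expressed per mL of the full mix and TMC per mL of Kybella, and neither denominator is named. The trial's premise is that its TMC is weaker than the regimen that caused atrophy and reduced efficacy. How much weaker depends on that unnamed denominator, and on the only basis that makes the 1.0 mg/mL label true there is no reduction. Any reading of efficacy or atrophy against the earlier study needs this settled.

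**Working it through.** **Inputs.** From Section 3: 10 mg SDOC per 1.2 mL; 0.2 mL per point; at most 50 points; the Group 2 recipe above. From Section 1: 0.05 mL of TMC at 40 mg/mL in 2.0 mL Kybella; 0.25 mL per point; up to 100 mg SDOC. The Kybella stock strength is not printed and is inferred in step 1.

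**1. Concentration.** Group 2 mix = 2.0 + 0.2 + 0.2 = 2.4 mL. SDOC = 10 / 1.2 = 8.333 mg/mL. The mix then holds 8.333 × 2.4 = 20 mg, which implies a stock of 20 / 2.0 = 10 mg/mL. On that stock the stated concentration is consistent with the recipe.

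**2. Dose per point.** 8.333 × 0.2 = 1.667 mg. The text gives 1.6 mg, which is 4% lower (1.6 / 1.667 = 0.96).

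**3. Maximum per session.** Volume = 50 × 0.2 = 10.0 mL. SDOC = 10.0 × 8.333 = 83.3 mg, or 50 × 1.6 = 80 mg. The stated maximum is 100 mg, so the shortfall is 16.7% (20% at 1.6 mg).

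**4. What would give 100 mg.** With 0.2 mL and 50 points held fixed, the strength must be 100 / 10.0 = 10 mg/mL, the undiluted stock from step 1. At 8.333 mg/mL, 100 mg needs 100 / 8.333 = 12.0 mL, that is 60 points of 0.2 mL or 50 points of 0.24 mL. Section 3 prints neither.

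**5. Area dose.** If each point is assigned 1 cm2 (an assumption), 1.667 mg per point is 1.67 mg/cm2 against the nominal 2, or 17% lower.

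**6. TMC in Group 2.** Amount = 0.2 × 10 = 2 mg. Per mL of Kybella: 2 / 2.0 = 1.0 mg/mL, which reproduces the label. Per mL of mix, the basis used for SDOC: 2 / 2.4 = 0.833 mg/mL.

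**7. TMC against the earlier study.** Amount in the earlier mix = 0.05 × 40 = 2 mg, in 2.0 + 0.05 = 2.05 mL.

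| Basis | Earlier study | Group 2 | Change |
|---|---|---|---|
| mg per mL of Kybella | 2 / 2.0 = 1.0 | 2 / 2.0 = 1.0 | 0% |
| mg per mL of mix | 2 / 2.05 = 0.976 | 2 / 2.4 = 0.833 | −15% |
| mg per point | 0.976 × 0.25 = 0.244 | 0.833 × 0.2 = 0.167 | −32% |
| Maximum mg per session* | 100 × 2 / 20 = 10 | 10.0 × 0.833 = 8.3 | −17% |

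*Assumes a 10 mg/mL stock in both studies and that the 100 mg cap binds in the earlier one.

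The 15% comes from added diluent alone. The 32% also reflects the smaller volume per point.

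**The case against.** The strongest reply is that 50 points and 100 mg are two separate ceilings. Section 1 lends this some support: with a 10 mg/mL stock, the earlier schedule comes to 50 × 0.25 × 9.76 = 122 mg, yet it too is capped at 100 mg. This stands to the extent that 83.3 mg breaches nothing, so a reader should not infer an overdose. It does not make the figures agree, because the maximum printed for this schedule cannot be reached with it. It is also true that Section 3 discloses the dilution, the per-point dose and the full Group 2 recipe, so a careful reader can recover the amounts.

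Several stronger readings are tempting, but the documents do not support them:

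- **The area dose falls short under any layout.** Neither the layout nor the area denominator is stated, and edge points matter in a bounded field. A 5 × 10 grid at 1.0 cm spans 4 × 9 = 36 cm2, giving 83.3 / 36 = 2.3 mg/cm2.
- **Lidocaine is mislabelled too.** In the full mix, 0.2 mL of 1% is 0.2 / 2.4 = 0.083%, which rounds to the 0.1% in Section 2.
- **The missing Group 1 Kybella volume is a separate error.** With the same stock, 10V / (V + 0.4) = 8.333 gives V = 2.0 mL.
- **SDOC per point also fell by 32% from the earlier study.** This needs a common stock strength, which the documents do not state.

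**Conclusion.** The point holds as an inconsistency in stated doses. On Section 3's own figures, each point delivers 1.67 mg SDOC (1.6 mg printed) and a full session at most 83.3 mg (80 mg at 1.6 mg), against a stated ceiling of 100 mg. The TMC strength is 0.83 mg/mL on the basis used for SDOC, against a label of 1.0 mg/mL. These results need only the printed figures. The area-dose gap of 17% rests on assigning 1 cm2 to each point.

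The consequence is for the rationale. TMC is 0%, 15% or 32% lower than in the earlier study according to the basis chosen, or 17% lower per maximum session under the two assumptions given, and the protocol does not choose. A reader might infer that TMC was not reduced at all; that is so only per mL of Kybella. A reader might also infer that the arms received different SDOC strengths. The documents do not support this: both groups state the same final concentration, and saline is added to Group 1 to keep them equal. The randomised comparison is not biased on this account.

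**What to change.** - In Section 3, reconcile the area dose, dose per point, number of points, volume per point and maximum total so that each follows from the others. Which figures stand is the sponsor's clinical decision.
- State the Group 2 TMC strength on the full mixed volume (0.83 mg/mL for the recipe as printed), or keep the label and name its denominator.
- In Sections 1 to 3, say on which basis TMC is lower than in the earlier study, and by how much.
- Report SDOC and TMC delivered in mg per session, calculated from the final concentration and the volume injected.

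The cost is mainly corrected text in Sections 1 to 3, handled as an amendment under Section 9.4, plus a record of the volume injected at each session if the case report form does not already capture it. Some printed figures may change, depending on which the sponsor keeps. No endpoint, sample size or analysis changes.

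### Section 3 states the diluted SDOC strength but does not carry it through: 50 points deliver at most 83.3 mg (not 100 mg), about 1.67 mg/cm² (not 2), with TMC at 0.83 mg/mL (not 1.0)

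*Combined protocol and SAP*

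**What the plan says.** Section 3 defines two groups.

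- **Group 2** is headed "Kybella(TM)+TMC at 1.0 mg/mL". The mix is 2.0 mL of Kybella, described as 2 mg/cm², with "0.2 mL of 10 mg/mL" triamcinolone and 0.2 mL of 1% lidocaine, "delivered in up to 50 injections spaced 1.0 cm apart at 0.2 mL/injection for a total dose of up to 100 mg of SDOC".
- **Group 1** has the same 2 mg/cm² description and 0.2 mL of 1% lidocaine, "plus 0.2cc saline to the non-TMC group to maintain equal concentrations in each injection". It is given in "up to 50 injections spaced 1.0 cm apart at 0.2 mL/injection for a total maximal dose of up to 100 mg of SDOC".
- **Both groups** have a stated final SDOC strength of "10mg/1.2mls or 1.6mg per 0.2 cc injection point".

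Section 2 describes the anaesthetic component thus: "Addition of 0.1% lidocaine will provide immediate pain relief for a better patient experience".

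On the number of TMC doses, section 3 says that at each site "10 will receive Kybella(TM) plus differing doses of triamcinolone acetate in the following way". One TMC group at one strength follows. The protocol title calls the trial dose-ranging, and the treatment lines at Visits 1, 4 and 7 in section 6 refer to varying TMC doses.

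**The concern.** The final strength in section 3 reflects the additives. The 100 mg maximum, the 2 mg/cm² and the 1.0 mg/mL TMC label do not appear to. If so, two kinds of harm follow.

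The first is in conduct. Section 3 is the dosing instruction for two sites. One site might hold to 0.2 mL per point, and another might raise the volume to reach 2 mg/cm². They would then give different amounts of both drugs under one protocol.

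The second is in reporting. A paper that repeats the printed figures would describe an SDOC dose that no patient received and a TMC strength that was never injected. Labels that promise several TMC doses would suggest dose-response information that a single strength cannot give.

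**Working it through.** **Inputs, all from section 3.** Kybella 2.0 mL; TMC 0.2 mL at 10 mg/mL (Group 2) or saline 0.2 mL (Group 1); lidocaine 0.2 mL at 1%, that is 10 mg/mL; 50 points of 0.2 mL; stated final SDOC strength 10 mg per 1.2 mL. The 1.0 cm spacing is taken as one point per cm².

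**Stock strength.** 10 mg per 1.2 mL is 20 mg per 2.4 mL. That 20 mg comes from 2.0 mL of Kybella, so the undiluted stock is 10 mg/mL.

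**Group 1 volume.** Section 3 does not state Group 1's Kybella volume V. From its additives and final strength, 10 × V/(V + 0.4) = 10/1.2, so V = 2.0 mL, as in Group 2.

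**Reproducing the printed figures.** They come out only if the additives are left out:

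- SDOC: 10 mg/mL × 0.2 mL = 2.0 mg per point (2 mg/cm²); × 50 = 100 mg.
- TMC: 0.2 mL × 10 mg/mL = 2.0 mg; 2.0 mg / 2.0 mL = 1.0 mg/mL.
- Lidocaine: 2.0 mg / 2.0 mL = 1 mg/mL = 0.1%.

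**Full mix.** Volume = 2.0 + 0.2 + 0.2 = 2.4 mL.

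- SDOC: 20 mg / 2.4 mL = 8.33 mg/mL; × 0.2 mL = 1.67 mg per point; × 50 = 83.3 mg. The protocol's 1.6 mg is this value truncated, and 1.6 × 50 = 80 mg.
- TMC: 2.0 mg / 2.4 mL = 0.833 mg/mL; × 0.2 mL = 0.167 mg per point; × 50 = 8.33 mg per session.
- Lidocaine: 2.0 mg / 2.4 mL = 0.833 mg/mL = 0.083%.

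| Quantity | Stated | From the mix |
|---|---|---|
| SDOC, 50 points | 100 mg | 83.3 mg (−17%) |
| SDOC per area | 2 mg/cm² | 1.67 mg/cm² |
| SDOC, three sessions | 3 × 100 = 300 mg | 3 × 83.3 = 250 mg |
| TMC strength, Group 2 | 1.0 mg/mL | 0.833 mg/mL |
| Lidocaine | 0.1% | 0.083% |

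**The conflict as an instruction.** Reaching 2 mg at each point needs 2/8.33 = 0.24 mL. A site doing that gives 0.24/0.20 = 1.2 times the SDOC and TMC of a site using 0.2 mL.

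**The earlier study (section 1).** Its printed recipe is 2.0 mL Kybella with 0.05 mL of 40 mg/mL TMC, given as 50 points of 0.25 mL, at 2 mg/cm² and up to 100 mg. Assuming the same 10 mg/mL stock:

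- *As printed:* 20 mg / 2.05 mL × 0.25 mL = 2.44 mg per point, × 50 = 122 mg. This does not match 2 mg/cm² or 100 mg. TMC:SDOC = 2.0/20 = 0.10, the same as Group 2 (2.0/20).
- *Kybella 0.2 mL instead of 2.0 mL:* 0.2 + 0.05 = 0.25 mL per point, 2.0 mg SDOC, × 50 = 100 mg. Exact fit. TMC is 0.05 × 40 = 2.0 mg per point; ratio 1.0.
- *TMC 0.5 mL instead of 0.05 mL:* 20 mg SDOC and 20 mg TMC in 2.5 mL; 0.25 mL holds 2.0 mg of each; × 50 = 100 mg SDOC. Exact fit; ratio 1.0.
- *Points of 0.2 mL instead of 0.25 mL:* 1.95 mg per point, 97.6 mg at 50 points. Near but not exact; ratio 0.10.

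**The case against.** The strongest defence is that the plan does not hide the dilution. Section 3 prints the diluted SDOC strength for both groups and adds saline to Group 1 so that the arms match. That stands: the fault is a conflict between figures in one section, not a failure to consider the diluent. It also stands that a stated maximum is a ceiling and that 83.3 mg does not breach it.

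Lidocaine at 0.083% rounds to 0.1% at the precision section 2 uses, so that figure is not an error.

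The dose-ranging wording is a labelling matter. Section 14 plans no dose-response analysis, and the two-arm allocation in section 3 is clear.

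A reader might go further and infer from section 1 that the TMC dose is not low at all, because the printed recipe of the earlier high-dose study has the same TMC:SDOC ratio as Group 2. The documents do not support that. The printed recipe contradicts its own stated totals. Both single-figure corrections shown above that fit exactly make the earlier ratio ten times Group 2's, which agrees with calling the present dose very low. One of them keeps 0.05 mL of TMC, so confirming that volume alone would not show that the doses are alike.

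What the defence does not answer is that 100 mg, 2 mg/cm² and 1.0 mg/mL cannot be obtained from the mix and point volume that section 3 prescribes.

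**Conclusion.** The point holds as an internal inconsistency in the dosing section, and it should be fixed. Taken as printed, the SDOC maximum and area dose are 20% above what the mix delivers (100/83.3; 2/1.67), and so is the TMC strength (1.0/0.833). The 83.3 mg follows directly from the plan's own final strength, point volume and point count. The 1.67 mg/cm² also assumes one point per cm².

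A reader might infer that the randomised comparison is biased or that patients would be overdosed. Neither follows. Both arms have the same SDOC dilution, and the delivered dose is below the ceiling. What is affected is the clarity of the dosing instruction, the accuracy of the reported doses, and comparison with SDOC given at a true 2 mg/cm².

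The dose-ranging, differing-dose and varying-dose labels are wrong, because one TMC strength is defined.

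The section 1 recipe is inconsistent as printed (about 122 mg against 100 mg, on an assumed 10 mg/mL stock). The documents cannot say which figure is wrong, so no conclusion about the relative TMC dose should rest on it yet.

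**What to change.** 1. Keep 0.2 mL per point. In both groups in section 3, state 1.67 mg SDOC per point, 1.67 mg/cm² and up to 83.3 mg per session. For Group 2, state TMC at 0.83 mg/mL, at most 8.33 mg per session. Give Group 1's Kybella volume (2.0 mL) explicitly.
2. Delete the dose-ranging wording in the title, the differing-dose wording in section 3, and the varying-dose wording at Visits 1, 4 and 7. Lidocaine may stay as about 0.1%.
3. Check the earlier study's recipe in section 1 against its source and correct it. Revisit the low-dose wording only if the source confirms both 2.0 mL of Kybella and 0.05 mL of TMC. Do not change the TMC dose on the 0.05 mL figure alone.

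The cost is one wording amendment and one source check, with no added patients, visits or measurements. Moving to 0.24 mL per point would deliver 2 mg/cm² and 100 mg, but it would raise exposure to both drugs by 20% over the current mix (TMC to 10 mg per session). That is a change of dose rather than a correction, and it works against the aim of using less steroid.

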# 4. STUDY POPULATION

#### 4.1 Number

Thirty (30), who satisfy all study inclusion criteria, and do not meet exclusion criteria, will be considered for entry into the study.

# 4.2 Study Endpoints

# a. Investigator Evaluations (Appendix A)

- The Clinician-Reported Submental Fat Rating Scale will be completed by a blinded-investigator on Visit Days 1, 30, 60, 90 and 180.
- The Submental Skin Laxity Grade (SMSLG) will be completed by a blinded-investigator on Visit Days 1, 30, 60, 90, and 180.
- A Side Effects Scale will be completed by a blinded-investigator at all follow-up visits. The side effects evaluated will include Edema, Erythema, Tenderness, Erosion/Ulceration, Steroid Atrophy, Induration, and Marginal Mandibular Palsy.

# b. Subject Evaluations (Appendix B)

- The Subject Evaluation of Side Effects Scale will be completed at Visits 2 through 11.
- The Subject Satisfaction Rating Scale will be completed by the patient on Visit Day 180.

# 4.3 INCLUSION CRITERIA

The following are requirements for a potential subject's inclusion into the study:

- 1. Females or Males in good general health age 18 65 years of age
- 2. Fitzpatrick skin types I-VI
- 3. Must be willing to give and sign a HIPAA form and informed consent form
- 4. Must be willing and able to comply with all study protocols and schedules
- 5. Must have submental fat graded by the investigator as 2 or 3 using the Clinician-Reported Submental Fat Rating Scale (PR-SMFRS)
- 6. Negative urine pregnancy test prior to each treatment (if applicable)

- 7. Female patients will be either of **non-childbearing potential** defined as:
  - 7.1 Having no uterus
  - 7.2 No menses for at least 12 months.

Or:

**(WOCBP)** women of childbearing potential must agree to use an effective method of birth control during the course of the study, such as:

- 7.3 Oral contraceptive pill, injection, implant, patch, vaginal ring, intrauterine device
- 7.4 Intrauterine coil
- 7.5 Bilateral tubal ligation
- 7.6 Barrier method used with an additional form of contraception (e.g., sponge, spermicide or condom)
- 7.7 Abstinence (If practicing abstinence must agree to use barrier method described above (7.6) if becomes sexually active)
- 7.8 Vasectomized partner (must agree to use barrier method described above (7.6) if becomes sexually active with unvasectomized partner)
- 8. Males must be willing to be clean shaven for all study visits
- 9. The patient must have had a stable weight (no fluctuation of >15 pounds in a year), diet, and physical activity for the previous 6 months

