# 6. STUDY PERIOD

# Visit 1 (Day 1, Baseline)

- Obtain written Informed Consent and HIPPA
- Record Medical History and Concomitant Medication
- Review Inclusion and Exclusion
- Record Subjects weight
- Randomization
- Pregnancy Test (If applicable)
- Photographs
- Blinded-Investigator Grade (CR-SMFRS) and (SMSLG)
- Treatment #1 with either Kybella(TM) alone or varying doses of TMC

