# 7.2 Unknown/Unforeseeable Risks

In addition to the risks listed above, there may be some unknown or infrequent and unforeseeable risks associated with Triamcinolone and/or Kybella(TM) injections. Patients will be informed both verbally and in writing in a timely manner of any new information, findings or changes to the way the research will be performed that might influence their willingness to continue their participation in this study.

**Pregnancy/Fetal Risks:** The effects of Triamcinolone and/or Kybella(TM) injections have not been studied in pregnancy and therefore **may be hazardous.** 

If a patient thinks that you may be pregnant or have become pregnant during the study the patient is to inform the study doctor immediately. If a patient becomes pregnant or thinks they may be pregnant, they will be removed from the study and the study doctor will refer the patient to seek obstetric care and may request to track their pregnancy and will report the pregnancy to the IRB.

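### Criterion 7.2 takes 12 months without periods as non-childbearing potential at any age from 18, so some women who could conceive may have no contraception requirement and no required pregnancy test

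*Combined protocol and SAP*

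**What the plan says.** Section 4.3 (Inclusion Criteria) sets the age range in its first criterion: "Females or Males in good general health age 18 65 years of age". Criterion 7 then sorts women into two alternatives. The first opens "Female patients will be either of non-childbearing potential defined as" and lists two entries, "7.1 Having no uterus" and "7.2 No menses for at least 12 months". The second follows after an *Or*: "women of childbearing potential must agree to use an effective method of birth control during the course of the study, such as". A list of methods runs from 7.3 to 7.8 and begins "Oral contraceptive pill, injection, implant, patch, vaginal ring, intrauterine device".

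Criterion 6 of the same section asks for a negative urine test before each treatment, again only if applicable. The schedule in Section 6 repeats the condition at each treatment visit; Visit 1 lists "Pregnancy Test (If applicable", and Visits 4 and 7 carry the same entry. The protocol does not say to whom the test applies.

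On risk, Section 7.2 (Unknown/Unforeseeable Risks) says that triamcinolone and/or Kybella "injections have not been studied in pregnancy and therefore" may be hazardous. It asks a patient who thinks she may be pregnant to tell the study doctor at once, and a pregnant patient is removed from the study.

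**The concern.** Absence of periods for a year is a reasonable sign of menopause only when nothing else explains it. Criterion 7.2 does not state that condition, and the age range covers all the reproductive years. Read as written, the criterion moves a woman out of the group that must use contraception on menstrual history alone, whatever the cause.

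What is at stake is fetal exposure to a treatment that the protocol itself describes as unstudied in pregnancy, at up to three injection sessions. The protocol's last line of defence is the woman's own suspicion that she is pregnant. It is weakest in this group, because a woman without periods has no missed period to alert her.

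**Working it through.** There is no figure to recompute. The check sets the eligibility, schedule and risk sections against each other.

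**Step 1: are 7.1 and 7.2 separate routes?** No conjunction joins them. If both were needed, 7.2 would add almost nothing, since a woman without a uterus does not menstruate. They are therefore read as alternatives, and 7.2 is sufficient alone.

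**Step 2: does any other text narrow 7.2?** Sections 4.3, 4.4, 5.1, 6 and 7.2 contain no menopause condition, no age floor above 18, no hormone confirmation and no exclusion of other causes.

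**Step 3: apply the text to individual cases.**

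| Woman | Meets 7.1 or 7.2 as written? | Contraception required? | Test required? | Other safeguard |
|---|---|---|---|---|
| No uterus | Yes (7.1) | No | Not needed | Not needed |
| Postmenopausal | Yes (7.2) | No | Not needed | Not needed |
| Age 25, ovulatory disorder, no contraception | Yes (7.2) | No | Unclear | Investigator discretion (Section 4.4, exclusion 5) |
| Age 30, periods stopped on a hormonal injection, implant or intrauterine device | Yes (7.2), and also uses a 7.3 method | Not if classed under 7.2 | Unclear | Protected while the method continues; not obliged to continue it |
| Recently gave birth, not breast feeding | Possibly (7.2) | Not if classed under 7.2 | Unclear | Weight-stability rule (Section 4.3, criterion 9) often excludes her |

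The third row is the clearest gap. The fourth is narrower: the woman is protected on entry, but nothing binds her to stay so.

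**Step 4: does the testing rule close the gap?** There are three treatments (Days 1, 30 and 60), each with a conditional test. The condition is undefined. Its natural meaning is childbearing potential, because testing a woman without a uterus would serve no purpose. On that meaning, a woman classed under 7.2 is not required to be tested. A site could still choose to test every woman with a uterus, so the supportable statement is that tests may be omitted at up to three visits.

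**Step 5: do the remaining safeguards close it?** Exclusion 1 in Section 4.4 bars pregnancy, breast feeding and planned pregnancy for every woman. It requires no test and cannot prevent an unplanned pregnancy. The reporting rule in Section 7.2 depends on the woman suspecting pregnancy. Neither replaces the contraception requirement or a scheduled test.

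**The case against.** The strongest reply is that competent sites will apply 7.2 as a menopause criterion. Visit 1 records medical history and concomitant medication, so the reason for absent periods should be visible. Users of hormonal methods are named in 7.3, and the natural reading of criterion 7 as a whole places them there. Much of this stands and makes the affected group small. It does not remove the gap: the text permits the other reading, and two sites would each have to supply the same unwritten condition.

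A reader might draw several stronger conclusions that the documents do not support:

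- *Every such woman misses all three tests.* The condition on testing is undefined and is not linked to 7.2, so omission is possible but not established.
- *Women on hormonal methods go without contraception.* They are using a method that 7.3 accepts. The defect is only that nothing obliges them to continue.
- *The two branches impose opposite requirements.* Criterion 7.2 imposes none, and the branches are alternatives. A woman who fits both still satisfies criterion 7; the problem is which class she falls in.
- *Recent childbirth is a common route through 7.2.* Criterion 9 requires stable weight, diet and activity, and exclusion 1 removes breast-feeding women. Few would remain.
- *Irregular periods, listed in Section 7.1 as a triamcinolone risk, make the history unreliable.* Criterion 7.2 looks back over the 12 months before entry, before any study injection.
- *The Day 180 outcome is at risk.* Any pregnancy leads to removal, tested or not. A test would not save the outcome; only contraception could, and the effect on the analysis is slight.

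**Conclusion.** The point holds as a gap in the wording of eligibility. As written, 7.2 can class a premenopausal woman with a uterus as of non-childbearing potential. She is then free of the contraception requirement and may not be required to have the test before any of the three treatments. This rests on two readings: that 7.1 and 7.2 are alternatives, and that the test is meant for women of childbearing potential.

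The documents do not give the number affected. Purely as an assumption, if 24 of the 30 subjects were women and 5% to 15% of them were premenopausal with a year of absent periods, the count would be 24 × 0.05 = 1.2 to 24 × 0.15 = 3.6, or about 1 to 4 women. A reader might take that as the number exposed, but it includes women already protected by their method. The unprotected number is smaller and may be zero.

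This is a participant-safety point, not a statistical one. The correction is worth making because it is cheap and the protocol itself describes a possible fetal hazard.

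**What to change.** Make three wording changes:

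1. In Section 4.3, reword 7.2 as postmenopausal: a year or more since the last period, with no other cause. Hormonal contraception, recent pregnancy or lactation, and an ovulatory disorder can serve as examples of other causes.
2. State in criterion 7 that any other woman with a uterus is of childbearing potential, so that criterion 6 and the contraception list in 7.3 to 7.8 apply to her.
3. Define *if applicable*, in criterion 6 and at Visits 1, 4 and 7, as all women of childbearing potential.

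The cost is a short amendment, a few more urine tests of a kind already in the schedule, and a contraception commitment for a few women who would otherwise have none. Sample size, visits and analysis do not change.
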